#### J.6.a. PROCEDURES FOR DISCONTINUATION FROM STUDY TREATMENT

#### J.6.a.1. MEDICAL REASONS FOR DISCONTINUATION

In the event that the patient's blood pressure rises to an unacceptable level during treatment, in the opinion of the attending physician, the physician will discontinue treatment and initiate appropriate measures according to usual medical practice.

A patient who decides to discontinue participation in the study will always be asked about the reason(s) and the presence of any AEs. If possible, they will be seen and assessed by an investigator. AEs will be followed up until resolution (see Section I.4.b).

If a patient discontinues from the study before randomization, then no further follow-up will be expected. However, if the patient discontinues after randomization, but before receiving any study treatment, the patient will be asked to return for a final study visit, during which the procedures outlined in the Early Termination Visit procedures will be completed, including AEs and concomitant medication assessments.

If a patient discontinues from the study before completion and has received a dose of study drug, the patient will be asked to return for a final study visit, at which the procedures outlined in the Early Termination Visit will be completed. Every effort should be made to follow up with patients who discontinue from the study prior to Visit 11 (Day 28). If patients refuse to return to the clinic for the study-related assessments, a modified follow-up through, for example, regular telephone contact or a contact at study closure should be arranged, if agreed to by the patient and in compliance with local data privacy laws/practices. If the patient refuses follow-up, the reason for the refusal and last contact date should be documented in the eCRF and source documents.

Patients who discontinue from the study will not be replaced.

#### J.7. UNBLINDING PROCEDURE

##### J.7.a. METHODS FOR ENSURING BLINDING

The investigator, patient, and study staff will be blinded. Packaging and labeling of the study drugs will be performed in a way to ensure blinding throughout the study.

No members of the study team at study sites will have access to the randomization scheme during the conduct of the study.

The randomization schedule for blinding of randomized treatment will be maintained by MGH CTNI or representative and will not be disclosed until after database lock.

##### J.7.b. METHODS FOR UNBLINDING THE STUDY

Individual treatment codes, indicating the treatment randomization for each randomized patient, will be available to the investigator(s) or pharmacists from MGH CTNI or its designee.

The treatment code must not be broken except in medical emergencies when the appropriate management of the patient necessitates knowledge of the treatment randomization. The investigator documents and reports the action to MGH CTNI or representative, without revealing the treatment given to the patient to MGH CTNI or representative's staff.

MGH CTNI retains the right to break the code for serious adverse events (SAEs) that are unexpected and are suspected to be causally related to a study drug and that potentially require expedited reporting to regulatory authorities. Treatment codes will not be broken for the planned analyses of data until all decisions on the evaluability of the data from each individual patient have been made and documented.

## K. ETHICAL CONSIDERATIONS

### K.1. RISK/BENEFIT ASSESSMENT

#### K.1.a. POTENTIAL RISKS

Participants must be capable of understanding the nature of this study, its potential risks, discomforts and benefits. Study physicians will obtain consent after they have fully explained the study purpose and its procedures, and potential participants have demonstrated an understanding of the protocol, willingness to participate, and competency to consent.

#### K.1.b. SAFETY

Ketamine was well tolerated after single-dose administration up to 60.0 mg, multiple-dose administration up to 35.0 mg, and single-dose administration up to 25.0 mg. There were no deaths or SAEs reported in any published study. One (1) subject was discontinued due to a treatment-related AE of mild ventricular tachycardia in one study, and no subjects were discontinued due to AEs in two other studies. The most common AEs considered by the investigator to be related to ketamine (occurring >1 incidence) were: headache (6 events), diarrhea (4 events), nausea (3 events), and anxiety (2 events), dyspepsia (5 events), pruritus generalized (3 events), headache (2 events), diarrhea (2 events), and abdominal pain (2 events). In these three studies, there were no clinically significant values, changes, or trends in clinical laboratory data. No clinically significant changes were observed in the hypothalamic-pituitary-adrenal axis hormones of cortisol, prolactin, and luteinizing hormone. There were no clinically significant changes in vital signs and electrocardiograms (ECGs), including no evidence of changes in corrected QT (QTc) prolongation.

The most frequent adverse events with brexpiprazole are akathisia, headache, and weight increase. Mean changes from baseline in Abnormal Involuntary Movement Scale and Barnes Akathisia Rating Scale total scores are significantly greater with brexpiprazole 3 mg versus placebo.

#### K.1.c. CONFIDENTIALITY AND LOSS OF PRIVACY

The risk of loss of privacy is judged to be minimal. Confidentiality will be maintained by numerically coding all data, by disguising identifying information, and by keeping all data in locked file drawers or on password-protected databases on password-protected and encrypted computers in locked offices. Subject information will be accessible only to research staff. Information about study participants will not leave our institution in any form that would identify individual subjects. Sites will enter subject data directly into the study database, which will be managed by the MGH CTNI team. Subjects will be assigned study ID numbers.

#### K.1.d. PLANNED PROCEDURES FOR PROTECTING AGAINST OR MINIMIZING POTENTIAL RISKS

Participants must be capable of understanding the nature of this study, its potential risks, discomforts and benefits. Study physicians will obtain consent after they have fully explained the study purpose and its procedures, and the potential participant has demonstrated an understanding of the protocol, willingness to participate, and competency to consent. Confidentiality will be maintained by numerically coding all data, by disguising identifying information, and by keeping all data in locked file drawers or on password-protected databases on password-protected and encrypted computers in locked offices. Subject information will be accessible only to research staff. Information about study participants will not leave our institution in any form that would identify individual subjects. Data will be transmitted with subjects identified by code.

Regarding confidentiality and privacy, the risk of loss of privacy is judged to be minimal. Confidentiality will be maintained by numerically coding all data, by disguising identifying information, and by keeping all data in locked file drawers or on password-protected databases on password-protected and encrypted computers in locked offices. Subject information will be accessible only to research staff. Information about study participants will not leave our institution in any form that would identify individual subjects. Data will be transmitted with subjects identified by code.

#### K.2. JUSTIFICATION OF THE USE OF PLACEBO ARM

MDD is a serious illness. The decision to conduct placebo-controlled trials was carefully considered. Randomized trials utilizing a placebo control group are the gold standard for the establishment of treatment efficacy. The use of a placebo treatment is a method of providing a control group in the study design, minimizes investigator bias in assessments, promotes retention of the control group, and controls for the natural course of the disease (Vickers and deCraen, 2000). Therefore, lack of adequate control comparisons would limit the contribution of the data from this trial.

#### K.2.a. CLINICAL MONITORING OF SUBJECTS AND MANAGEMENT OF CLINICAL DETERIORATION AND EMERGENCE OR WORSENING OF SUICIDAL IDEATION

All patients will receive monitoring for clinical deterioration, support, attention, and reassurance in the context of a therapeutic alliance. By definition, the target population is one in which subjects have not responded to available antidepressant therapies. Both active treatment and placebo/control groups in each trial will receive comprehensive evaluation and careful monitoring. Close monitoring by a trained psychiatrist is beneficial for individuals with mood disorders. If patients are in need of more intensive psychiatric treatment at any time during the course of the trial, study personnel will assist in needed evaluation and referral to appropriate treatment settings. Subjects will be carefully monitored regarding depressive and other psychiatric symptoms. Non-responders to study treatment will be offered referrals for treatment at the end of the trial.

#### K.3. INFORMED CONSENT

The Investigator must ensure that patients are clearly and fully informed about the purpose, potential risks, and other critical issues regarding clinical trials in which they volunteer to participate. Preparation of the consent form is the responsibility of the Investigator and must include all elements required by CFR 21 Part 50.25 and the local IRB.

All subjects will receive the consent form for the study. These documents will be read by the patients and also reviewed by the patient with a clinician on the research staff prior to participating in the study. Any questions, concerns, or ambiguities will be clarified by the site's PI or another study clinician prior to the patient signing consent. Patients will sign informed consent and only then will begin participation in the study.

#### K.4. IRB REVIEW

Before study initiation, the Investigator must have written and dated approval/favorable opinion from the IRB for the protocol, consent form, patient recruitment materials/process (e.g., advertisements), and any other written information to be provided to patients.

The Investigator should provide the IRB with reports, updates, and other information (e.g., Safety Updates, Amendments, and Administrative Letters) according to regulatory requirements and Institution procedures.

A detailed list of required regulatory documents also to be submitted to MGH CTNI will be sent upon final approval of the protocol.

#### K.5. POTENTIAL BENEFITS TO STUDY PARTICIPANTS AND OTHERS

Potential benefits of the research to participants and others: This study will potentially help individuals with TRD. If we discover that this intervention is effective, these results will lead to a full clinical development program of this treatment for TRD.

Risks to subjects relative to the anticipated benefits to research participants and others: The treatment has been selected with consideration of safety in mind. Additionally, exposure to the intervention will be brief and carefully monitored. The risks of participation in the study are therefore judged to be small, and adequate protections are in place to monitor the medical wellbeing of participants. In contrast, the morbidity and mortality associated with TRD risks are well known to be very high, given the long-term disability associated with MDD.

Because of the tremendous public health impact of depression, if these treatments are shown to be effective for TRD, they could reduce the burden of depression-related morbidity and mortality.

Risks to subjects in relation to the importance of the knowledge that reasonably may be expected to result: The aforementioned data suggest that risks to subjects are minimal. The benefit to society from the development of efficacious interventions with rapid onset for TRD would be a substantial public health benefit.

## L. DATA HANDLING AND RECORD KEEPING

### L.1. COMPLETION OF ECRF

An Investigator is required to prepare and maintain adequate and accurate case histories designed to record all observations and other data pertinent to the investigation on each individual treated with the investigational product or entered as a control in the investigation.

### L.2. PROCEDURE FOR CORRECTIONS

An EDC system will be built for the study. The EDC system will include eCRFs designed to capture study information, which are completed by trained site staff. Specific details of the procedures for Data Management are found in the Data Management Plan and details regarding the EDC system training process can be found in the Study MOP.

### L.3. RECORD RETENTION

The Investigator must retain investigational product disposition records, case report forms, and source documents for the maximum period required by applicable regulations and guidelines, or Institution procedures, and at least for 10 years.

If the Investigator withdraws from the study (e.g., relocation, retirement) the records shall be transferred to a mutually agreed upon designee (e.g., another Investigator, IRB).

#### L.4. DATA CONFIDENTIALITY

Potential risks to data confidentiality will be mitigated by requirements for the de-identification of all study data and by security protocols for all data capture systems. All users of the EDC system will be tracked and provided access in a secure fashion following established SOPs for this process.

As with all research data, information gathered by the study will be used only for aggregate analysis; it will not be released with any information that identifies research participants. The data managers, statistician, Investigator, and Sponsor do not have access to the identities of patients. That information is retained only at the clinical centers. Uses and risks related to data collection will be outlined in the informed consent and reviewed with the subjects.

### M. MONITORING AND OVERSIGHT

#### M.1. EVALUATION OF STUDY SITES

Potential study sites have been evaluated by MGH CTNI to determine suitability for the proposed study. Information reviewed included, but was not limited to, facility details and site capabilities, past performance in similar studies, investigator, and staff experience, ongoing studies at the site, projected enrollment in this study, and FDA or other agency audit findings. Study sites may be asked to complete a study-specific Site Selection Questionnaire and other documents for consideration for participation and MGH CTNI or clinical study monitors may make a Site Qualification Visit prior to completing the evaluation process.

#### M.2. INITIATION OF STUDY SITES

Prior to subject enrollment, a study initiation visit will be completed at each investigational site to ensure the following: IRB approval has been obtained and documented prior to subject screening, the Investigators and study personnel are appropriately trained and clearly understand the study, the Investigators and study personnel accept the obligations incurred in undertaking this clinical investigation.

#### M.3. PERIODIC MONITORING VISITS

Qualified MGH clinical monitors or qualified contract monitors representing MGH CTNI will conduct investigational site monitoring visits to ensure that all Investigators conduct the study in compliance with the protocol and applicable regulations. The site will receive notification prior to each monitoring visit during the course of the study. It is expected that the Investigator and/or sub-Investigator and other appropriately trained study staff are available on the day of the visit in case any questions might arise.

Periodic monitoring visits will be made in accordance with the approved monitoring plan at all active study sites throughout the clinical study to assure that the Investigator obligations are fulfilled and all applicable regulations and guidelines are being followed. These visits will assure that the facilities are still acceptable, the protocol and investigational plan are being followed, the IRB has been notified of approved protocol changes as required, complete records are being maintained, appropriate and timely reports have been made to the Sponsor and the IRB, and the Investigator is executing all agreed activities.

MGH CTNI retains the right to remove either the investigator or the investigational site from the study for issues of non-compliance with the protocol or regulatory requirements.

On one or more occasions, the study site may be inspected or audited by the MGH CTNI representative or a third party. The Investigator will be informed in advance of this visit.

#### M.4. STUDY CLOSEOUT VISIT

Upon completion of the clinical study (when all subjects at the site have completed follow up visits, all data has been entered in the EDC system and cleaned, all queries resolved, and final electronic signatures have been obtained), a study closeout visit will be performed. Any unused study materials and equipment will be collected and returned to MGH CTNI. The Monitor will ensure that the Investigator's regulatory files are up to date and complete and that any outstanding issues from previous visits have been resolved. Other issues which will be reviewed at this visit include: discussing retention of study files, possibility of site audits, publication policy, and ensuring that the Investigator will notify the IRB regarding study closeout.

#### M.5. DIRECT ACCESS TO SOURCE DATA/DOCUMENTS

Subcontracts with study sites will specify that MGH CTNI or its representatives will have direct access to source data and documents for study monitoring. Additionally, NIMH, and the site IRBs may review source data following appropriate guidelines for this process.

#### M.6. INTERIM ANALYSIS

No interim analysis is planned for this study.

#### M.7. MEDICAL MONITORING

The medical monitor for this trial will be an M.D. designated by MGH CTNI. Throughout the course of the study the MGH CTNI Medical Monitor will review all adverse events, review issues related to subject eligibility, and assess the benefits and risks of protocols on an ongoing basis.

In addition, the Medical Monitor will be available for site questions. The Medical Monitor will be available to sites for questions regarding inclusion/exclusion criteria, protocol conduct, and safety.

Trained and qualified MGH CTNI staff physicians will be available to provide coverage during times when the Medical Monitor is unavailable. Sites will be provided with the Medical Monitor's cell phone number for emergency situations. Otherwise, sites are instructed to contact the Medical Monitor through email. All communications with sites will be documented by the Medical Monitor and kept in a file managed by the MGH CTNI Research Assistant, and reviewed periodically by the MGH CTNI Program Manager.

Each month the Medical Monitor will receive a listing of protocol violations for review and identification of possible trends.

Serious adverse events and clinically significant suicidal ideation or behavior will be reported by the site within 24 business hours of their knowledge of the event. For reportable (unexpected and/or related) serious adverse events and clinically significant suicidal ideation or behavior, the Medical Monitor will contact the Sponsor-Investigator within 48 business hours of the notice by the site. In addition, the Medical Monitor may request individual patient records, including laboratory data, clinical records, and other study related data, to evaluate these events against the known safety profile of the study treatment and the disease. Any records sent to the Medical Monitor by the site will be redacted for any identifying information before transmission. The Medical Monitor may recommend actions including partial or complete unblinding, and/or modifying or terminating the study. In addition to safety monitoring, the Medical Monitor may review enrollment data, demographic information, retention status, and other reports prepared by the study statistician that describe study performance and progress. The Medical Monitor will provide a report to the sSponsor-Investigator that describes study safety, progress and performance and provide recommendations regarding safe continuation or early termination of the trial. After review and evaluation of the specified periodic reports prepared by the statistician, the Medical Monitor will prepare a summary cover letter, according to pre-specified criteria, for submission to the Sponsor-Investigator. The letter will provide comments on the report, discuss any concerns or suggestions for change, and recommend continuation or cessation of the trial.

Urgent Clinical Situations: During the course of the study, a patient will be reassessed for continued participation based on clinical judgment of the investigators. All subjects will be offered access to 24/7 coverage for medical emergencies through the clinical staff at each site. Treatment options and their risks and benefits, including continued study participation and other treatment options, will be sensitively explained. All investigators have extensive clinical experience in the treatment of MDD and TRD, and can make the decision (while blinded) as to removal of subjects from the trial, particularly in the event of clinical deterioration or emergence/worsening of suicidal ideation. When a patient is removed from the trial based on clinical judgment, investigators will implement an appropriate treatment plan and arrange for follow-up for the patient.

## N. DATA ANALYSIS

To analyze the primary outcome data, we will use a linear mixed model for the observations taken at baseline, and subsequent visits, with terms for visit, and visit\*treatment for visits other than baseline, the primary contrast of interest being the difference between the two weeks (Day 14) value for active treatment and placebo. To address missing data, we will use all available data and use a restricted maximum likelihood estimation procedure, as implemented by SAS Proc MIXED. The model will include a site, a site\*time effect and a site\*time\*treatment interaction. The latter will be removed if not significant. Number of comorbid medical and psychiatric disorders and duration of illness, as measured prior to randomization, will be included as covariates. For the continuous secondary efficacy variables, the same approach as for the primary efficacy variable will be used for the analysis.

Power analysis: the sample size was chosen to ensure 80% power to detect an effect size of 0.8 on the SDQ between brexpiprazole plus intranasal ketamine treatment and placebo at a two-sided 0.05 significance level. This assumes the randomization of 52 subjects (26 subjects per arm).

O. PROTOCOL SIGNATURE PAGE

I have read this protocol and agree to adhere to the requirements. I will provide copies of this protocol and all pertinent information to the study personnel under my supervision. I will discuss this material with them and ensure they are fully informed regarding the conduct of the study according to 21 CFR parts 50, 54, 56 and 812, 45 CFR 46, to GCP as described in ICH guideline E6 and to hospital Institutional Review Boards.

\_\_\_\_\_  
Clinical Site

\_\_\_\_\_  
Principal Investigator Signature

\_\_\_\_\_  
Date

\_\_\_\_\_  
Principal Investigator  
Printed Name

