## C. STUDY SYNOPSIS

Title of Study:	A Double-Blind, Placebo-Controlled Study of Brexpiprazole plus Ketamine in Treatment-Resistant Depression (TRD)
Objective:	To evaluate the efficacy, safety, and tolerability of brexpiprazole in combination with intranasal ketamine (40 mg biweekly for 2 weeks and weekly for 2 weeks), compared to placebo, as a rapidly acting treatment for TRD
Methodology:	This is a multi-site, double-blind, placebo-controlled study of the acute efficacy of brexpiprazole or placebo in combination with intranasal ketamine added to ongoing, stable, and adequate antidepressant therapy (ADT) in the treatment of adults with MDD with TRD.
Number of Patients:	52 Patients
Diagnosis and Main Criteria for Inclusion:	Male and female outpatients (aged 18 to 65 years) who meet DSM-5 ( Diagnostic and Statistical Manual of Mental Disorders , Fifth Edition) criteria for MDD, have a current depressive episode of at least 8 weeks, and meet all of the following criteria: 

• <50% response to current antidepressant treatment (at least 8 weeks at an adequate dose, stable dose for at least 4 weeks)

• >1 and <8 failed trials in the current episode as per MGH ATRQ

• MADRS <math>\geq</math> 20 at screening and at baseline

• Good general health

• BMI= 18-35 kg/m^2

• Willing to use birth control if the patient is of child bearing potential

Test Product, Dosage, and Mode of Administration:	Subjects will be randomly assigned to one of two arms in a 1:1 fashion: brexpiprazole 0.5-3 mg/day or placebo for four weeks in combination with bi-weekly administration of intranasal ketamine (40 mg) for two weeks, and then weekly administration of intranasal ketamine (40 mg) for two weeks.
Visit Schedule:	Screening Visit, Baseline visit (Visit 1), Visits 1 and 2 days after the Baseline Visit (Visits 2 and 3), and then every 3 days after that for 26 days, with end of study visit one week after the last double-blind visit.
Primary Outcome Measure:	Symptom improvement will be evaluated by assessing changes in the SDQ.
Secondary Outcome Measures:	MADRS, HAMD-6, CGI-S, CGI-I.

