## F. OBJECTIVES

### F.1. PRIMARY AIM OF THE KETAMINE-BREXPIRAZOLE TRIAL

The primary objective is to investigate whether the degree of improvement in SDQ total score on brexpiprazole (initial dose .5 mg/day titrating to 3 mg/day over 21 days) is superior to placebo when combined with intranasal ketamine in the acute treatment of patients with TRD at two weeks (Day 14), when added to ongoing and stable antidepressant therapy with respect to the study primary outcome measure. Superiority will be demonstrated by a statistically significant greater decrease ( $p < 0.05$ , 2-sided) on the SDQ total score for patients receiving brexpiprazole versus placebo therapy.

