**TABLE 2– OVERVIEW OF STUDY SCHEDULE**

Screen Visit	Screening Period	V1 / Baseline Visit	V2	V3	V4	V5	V6	V7	V8	V9	V10	V11
Day -28 to Day -7	Taper (opt.) 5 half-lives of excluded psychotropic drug(s)	Day 0	Day 1	Day 2	Day 5	Day 8	Day 11	Day 14	Day 17	Day 21	Day 23	Day 28
		Baseline Assess.	Assess.	Assess.	Assess.	Assess.	Assess.	Assess.	Assess.	Assess.	Assess.	Assess.
		Intranasal Ketamine Admin.	Assess.	Assess.	Intranasal Ketamine Admin.	Intranasal Ketamine Admin.	Intranasal Ketamine Admin.	Intranasal Ketamine Admin.	Assess.	Intranasal Ketamine Admin.	Assess.	Assess.
		Study Drug*	Study Drug*	Study Drug*	Study Drug*	Study Drug*	Study Drug*	Study Drug*	Study Drug*	Study Drug*	Study Drug*	Study Drug*

\*Brexipiprazole or Placebo

Subjects will be screened for eligibility as detailed above. Study participants will be consented prior to the administration of any procedure or wash-out. Following a washout period, under the close supervision and monitoring of the study clinicians, for patients on psychotropic drugs (with the exception of ongoing antidepressant therapy and of ongoing hypnotic therapy), baseline assessment, MGH CTNI remote interview, and re-confirmation that all criteria for entry into the study are met, eligible subjects will be randomly assigned to one of two arms: brexpiprazole plus intranasal ketamine (n=25) or placebo plus intranasal ketamine (n=25). The brexpiprazole dose will be titrated in the following manner: 0.5 mg/day during the first week, at the Visit 5/Day 8 visit, the dose will be increased to 1 mg/day, at Visit 7/Day 14 the dose will be increased to 2 mg/day, and at Visit 9/Day 21, the dose will be increased to 3 mg/day. If the dose escalation is not tolerated, patient can go back to previous dose (fixed-flexible dose escalation). As per Table 2, all subjects will be followed for 28 days to examine the efficacy and tolerability of brexpiprazole plus intranasal ketamine’s effects. The study assessments will be performed at Days 0, 1, 2, 5, 8, 11, 14, 17, 21, 23, and 28 to assess the safety and efficacy of brexpiprazole plus intranasal ketamine compared to placebo plus intranasal ketamine treatment therapy in depressed patients who have demonstrated an inadequate response

to at least 2 adequate antidepressant therapies (ADTs) during the current MDE. Intranasal ketamine (40 mg) will be administered after all the assessments are completed on Days 0, 5, 8, 11, 14, and 21.

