#### I.1.h. VISIT 5 (DAY 8)

The patient should be instructed to refrain from eating and avoid alcohol as well as opioid and narcotic analgesics the day of the baseline visit (after midnight), as well as benzodiazepines within 2 hours of the intranasal administration. For visits in the afternoon, patients may have a light meal in the morning no less than 3 hours before the study visit.

Upon arrival, the patient will be administered the SDQ, the HAM-D6, the MADRS, the CGI-I, the CGI-S, and the CHRT. Following completion of these scales, the procedures listed in Table 3 should be completed.

The procedures for administration of ketamine and dispensation of blinded study drug will be the same as in section I.1.d. , and the Manual of Operations for the study.

I.1.i. VISIT 6 (DAY 11)

The patient should be instructed to refrain from eating and avoid alcohol as well as opioid and narcotic analgesics the day of the baseline visit (after midnight), as well as benzodiazepines within 2 hours of the intranasal administration. For visits in the afternoon, patients may have a light meal in the morning no less than 3 hours before the study visit.

Upon arrival, the patient will be administered the SDQ, the HAM-D6, the MADRS, the CGI-I, the CGI-S, and the CHRT. Following completion of these scales, the procedures listed in Table 3 should be completed.

The procedures for administration of ketamine and dispensation of blinded study drug will be the same as in section H.1.d. , and the Manual of Operations for the study.

I.1.j. VISIT 7 (DAY 14)

The patient should be instructed to refrain from eating and avoid alcohol as well as opioid and narcotic analgesics the day of the baseline visit (after midnight), as well as benzodiazepines within 2 hours of the intranasal administration. For visits in the afternoon, patients may have a light meal in the morning no less than 3 hours before the study visit.

Upon arrival, the patient will be administered the SDQ, the HAM-D6, the MADRS, the CGI-I, the CGI-S, and the CHRT. Following completion of these scales, the procedures listed in Table 3 should be completed.

The procedures for administration of ketamine and dispensation of blinded study drug will be the same as in section H.1.d. , and the Manual of Operations for the study.

I.1.k. VISIT 8 (DAY 17)

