#### J.3.b. BLINDED BREXPIRAZOLE/PLACEBO THERAPY

Blinded study drug will be provided to each subject at Visits 1, 5, 7 and 9, and a pill count will be performed by study site personnel at each study visit. Patients will be instructed to bring their pill bottles to every visit.

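### Does a Day 14 primary test misjudge a regimen that reaches 3 mg/day only at Day 21?

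*Combined protocol and SAP*

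**What the plan says.** The primary aim (Section F.1, repeated in Section E) asks whether "brexpiprazole (initial dose .5 mg/day titrating to 3 mg/day over 21 days) is superior to placebo when combined with intranasal ketamine" and continues without a break "in the acute treatment of patients with TRD at two weeks (Day 14), when added to ongoing and stable antidepressant therapy". The next sentence sets the criterion: "Superiority will be demonstrated by a statistically significant greater decrease" on the SDQ total score, two-sided p < 0.05. Section N fits a mixed model with visit-specific treatment terms, "the primary contrast of interest being the difference between the two weeks (Day 14) value for active treatment and placebo".

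The titration is in the text under Table 2 and in Table 6: 0.5 mg/day from Day 0, 1 mg/day from Visit 5 (Day 8), then "at Visit 7/Day 14 the dose will be increased to 2 mg/day", and 3 mg/day from Visit 9 (Day 21). Section J.3.b ties supply to the same visits: "Blinded study drug will be provided to each subject at Visits 1, 5, 7 and 9". The visit instructions, worded alike for Visit 7 in Section I.1.j, put the scales first: "Upon arrival, the patient will be administered the SDQ, the HAM-D6, the MADRS, the CGI-I, the CGI-S, and the CHRT". Section I.2.d.2 gives the SDQ a recall period of three days.

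Sections E and F.2 carry SDQ aims at Day 2 (Secondary Aim 1) and Day 28 (Secondary Aim 2), each with its own p < 0.05 criterion. The Synopsis states the objective as evaluating the combination "compared to placebo, as a rapidly acting treatment for TRD".

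**The concern.** The treatment named in the primary aim and the exposure behind the primary measurement differ. The name includes a 3 mg endpoint, but the measurement comes before the 2 mg step. The only brexpiprazole efficacy doses cited in the background (Section D.2.b) are 2 and 3 mg once daily, added to antidepressant therapy without ketamine.

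Two misreadings seem possible. A null Day 14 result could be reported as failure of a regimen whose upper steps had not been taken. A positive one could be reported as superiority of the regimen up to 3 mg. Section K.5 links a finding of effectiveness to a full development program, so the reading could matter. No sentence says in so many words that the Day 14 result describes early titration only, or which contrast speaks for the regimen after the later steps.

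**Working it through.** **The plan's own figure.** Inputs from Section N: standardized effect 0.8, two-sided alpha 0.05, power 80%, 26 per arm.
- Normal approximation: n per arm = 2(1.960 + 0.842)² / 0.8² = 24.5, rounded up to 25.
- Two-sample t test: 25.5, rounded up to 26 per arm, or 52 in all. Power at 26 per arm is 80.7%.

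The stated 52 reproduces, and nothing in the concern alters it.

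**Exposure before the Day 14 SDQ, nominal days.** One dose a day, with the Visit 7 dose not counted because the step up follows that visit's dispensing.
- Days 0 to 7: 8 × 0.5 = 4 mg
- Days 8 to 13: 6 × 1 = 6 mg
- Total by Day 14: 10 mg, with 0 days at 2 mg or more
- Days 14 to 20: 7 × 2 = 14 mg. Days 21 to 27: 7 × 3 = 21 mg
- Four-week total: 10 + 14 + 21 = 45 mg, and 10/45 = 22%

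**Exposure over the visit windows in Table 3.** Visit 5 falls on Days 6 to 10 and Visit 7 on Days 12 to 16. The planned amount by Visit 7 is 0.5 × V5 + (V7 − V5) = V7 − 0.5 × V5.
- Minimum: 12 − 0.5 × 10 = 7 mg
- Maximum: 16 − 0.5 × 6 = 13 mg

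Each step moves with its visit, so time at 2 mg or more is zero throughout. The factual part of the concern is right.

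**Exposure by Visit 11.** Nominally 7 days at 2 mg and 7 at 3 mg. For a patient who takes every step, time at 2 mg or more is V11 − V7, at least 24 − 16 = 8 days. Time at 3 mg is at least 2 days, because Visit 10 lies between Visits 9 and 11. The Visit 9 bottle covers 30/3 = 10 days. Section J.4 allows a return to the previous dose. Day 28 therefore informs the flexible four-week regimen, not 3 mg as such.

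**Do the passages conflict?**

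| Item | E and F | Table 2 text and Table 6 | N |
|---|---|---|---|
| Titration | to 3 mg over 21 days | 3 mg at Day 21 | – |
| Primary time | Day 14 | – | Day 14 |
| Later time | Day 28 SDQ, own criterion | – | same model family |

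They agree. F.2 also attaches the same dosing description to the Day 2 aim, when only 0.5 mg can have been taken. The description works throughout as a label for the randomized arm, and the time point in each aim limits the claim.

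**What a change would buy.** An interpretive sentence changes no estimate, test or sample size. The substantive alternative is a Day 28 primary. Ketamine is given on Days 0, 5, 8, 11, 14 and 21, after that day's assessments. The Day 14 SDQ therefore comes 14 − 11 = 3 days after the last ketamine dose and closes the two-week biweekly phase. The Day 28 SDQ comes 28 − 21 = 7 days after the last dose. The two time points answer different questions.

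**The case for a change.** The best case for acting is that it is cheap and must be done early. Stating a time point and a titration side by side is not the same as stating the limit that follows. A sentence written before unblinding is credible, while the same sentence after a null result looks like an excuse. Safety is described over the full four weeks, so an unqualified claim would pair efficacy at 1 mg/day or less with safety data that extend to 3 mg.

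The exposure facts stand, and so does the remark about timing. But the case needs a reader who overlooks Day 14 in the very sentence that makes the claim. The contrast said to be missing exists: Secondary Aim 2 tests the same arms on SDQ at Day 28, and it does not depend on the Day 14 result. Promoting Day 28 to first secondary would displace Day 2, which Section E lists as Secondary Aim 1.

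A second argument is that a low dose may mean a small effect. If the true Day 14 effect were 75%, 50% or 25% of 0.8, t-test power at 26 per arm would be 56%, 29% or 11%. Those fractions are assumptions. The documents give no dose-response, and no source or dose for the 0.8. They show what would be at risk if early exposure were too low to work, but not that it is. Accepting that risk in order to test for an early effect is the sponsor's choice.

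**Conclusion.** No change to the plan. Anyone following it as written obtains a valid randomized comparison of the two strategies at two weeks, and an unconditional secondary comparison at four weeks. The absent explanatory sentence is a gap that competent reporting fills: the Day 14 result, positive or null, describes the first two weeks of titration. The Day 28 SDQ aim informs the four-week flexible regimen, as secondary evidence. The Day 2 aims read the same way, for 0.5 mg.

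The size of the point is descriptive: 10 of 45 planned mg by Day 14 (7 to 13 mg over the windows), with no day at 2 mg or more. The effect on type I error, the estimate and N = 52 is nil. This assumes one dose a day, steps taken at the stated visits and the SDQ completed on arrival. Nothing here bears on which dose or schedule is right.
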